Section 8.3.2 Time period and frequency for collecting AE and SAE information previously referred to Appendix B for details of the time period for SAE reporting, procedures for completing and transmitting SAE reports. This reference is incorrect. This information is provided in section 8.4.1 Reporting of serious adverse events and so these incorrect references to Appendix B have been corrected to refer to section 8.4.1.

Section 8.4.5.2 Management of savolitinib-related toxicities – additional requirement for French sites only for clinical monitoring of savolitinib-related QTc prolongation NCI CTCAE Grade 3. The patient must remain hospitalised with continuous cardiac monitoring (ECG) until specialist advice is obtained by a cardiologist.

Section 8.7 (optional genomics initiative sample) – details of tube to be used removed (standard 6 ml EDTA tube). This level of detail is provided in the Central Laboratory Manual which is open to revision and is not required within the clinical study protocol.

The Sponsor management team will actively assess the safety and tolerability of the study treatment through continuous safety monitoring starting after the first 15 patients have had the opportunity to be treated for at least 6 weeks; see description in section 8.2 and section 9.5, also introduced in section 1.2. Intent to evaluate safety and tolerability of the study treatment by continuous monitoring of key patient information by the Sponsor (included in Section 8.2) is replaced with a more detailed proposal in planned statistical analyses in Section 9.2 of possible evaluation criteria of safety and tolerability of the study treatment at the planned interim analysis for assessment of efficacy. At the interim analysis (CCI [REDACTED]) it may be considered futile to continue the study if there is CCI % probability for the discontinuation due to any AE rate to be below the target value (CCI %). Additionally, once the first 15 patients have had the opportunity to be treated for at least 6 weeks a predictive power calculation will be used to assess the chance of observing a discontinuation due to any AE rate of CCI % or less and a discontinuation due to a hypersensitivity/anaphylaxis AE rate of CCI % or less.

Section 4.2.2 addition of possible assessment of the proportion of patients discontinuing study treatment due to any AE and the proportion of patients discontinuing due to AE of hypersensitivity/anaphylaxis to evaluate the safety and tolerability of savolitinib in

combination with osimertinib to the listing of standard safety parameters under rationale for study endpoints.

Appendix [I 3.4](#) recommendations for clinical management of hypersensitivity revised following review by the Sponsor of reported safety information for patients treated with the combination of savolitinib with osimertinib on the Phase I TATTION study. Investigators are recommended to continue treatment with savolitinib through initial mild symptoms of potential hypersensitivity with optimal supportive care rather than mandating immediate dose interruption and subsequent rechallenge. The rationale for this change in management is the Sponsor's observation that the majority of severe acute hypersensitivity reactions, including in some cases anaphylaxis, occurred following dose interruption and rechallenge.

If savolitinib dosing is interrupted, intense medical monitoring for restart at the institution is required with medical equipment readily available for resuscitation and management of anaphylaxis, vital status recording before and for at least 4 hours after dosing, 24 hour observation in the clinic prior to discharge. Should symptoms of potential hypersensitivity recur, or an acute anaphylactic reaction occur, immediate intervention must be instituted for appropriate management of the event and savolitinib must be permanently discontinued. These recommendations are guidelines only and final decisions concerning management of individual patients reside with the investigator or the treating physician. Clarification in the Benefit/risk assessment in Section [2.3](#) that these toxicity management guidelines apply to patients who experience hypersensitivity or pyrexia.

Clarification that Appendix [I 3.2](#) Dose modification guidelines due to savolitinib-related toxicity apply to general toxicities. Restart of savolitinib dosing following dosing hold due to NCI CTCAE Grade 3 or recurrence of Grade 3 toxicity must follow the specific restart guidelines if the event includes symptoms of pyrexia, skin reactions, myalgia, arthralgia, or hypersensitivity, as per section [I 3.4](#), added as footnote b to [Table 23](#) for NCI CTCAEs of Grade 3 or recurrence of Grade 3 toxicities.

Criteria to discontinue savolitinib dosing due to drug-related hepatotoxicity have been revised in Appendix [I 3.3.1](#) to clarify elevated ALT or AST $>8 \times$ ULN with total bilirubin elevation above baseline or ULN; or ALT or AST $>5 \times$ ULN for >2 weeks with total bilirubin elevation above baseline or ULN. Dosing should be withheld if ALT or AST $>5 \times$ ULN for >2 weeks or $8 \times$ ULN without total bilirubin elevation above baseline or ULN. Dosing should be withheld if ALT or AST $>3 \times$ ULN and concurrent total bilirubin $1.5 \times$ ULN. Dosing should be discontinued for recurrent ALT or AST $>3 \times$ ULN rather than >3 to $5 \times$ ULN; for total bilirubin $>1.5 \times$ ULN rather than >1.5 to $2 \times$ ULN; withheld for recurrent ALT or AST >3 rather than >3 to $5 \times$ ULN without total bilirubin elevation above baseline or ULN.

1 PROTOCOL SUMMARY

1.1 Schedule of activities (SoA)

The schedule of activities (SoA) at screening, treatment period, discontinuation, follow-up period and progression is shown in [Table 1](#). The SoA for patients who cross over to savolitinib 300 mg bid plus osimertinib from the savolitinib 300 mg bid plus placebo arm is shown in [Table 2](#).

Schedule of activities (SoA) for allocated / randomised treatment

Table 1 Schedule of Activities for allocated / randomised treatment

Visit	Pre-screening	Screening	Treatment Period				Follow-up ^a				Details in CSP section
			Cycle 1 (28-day cycle)		Cycles 2 to 6 (28-day cycle)	Cycle 7 onwards (28-day cycle)	Treatment Discontinuation Visit	28-day Follow-up Visit ^b	Progression Follow-up ^c	Survival Follow up	
Week (Day 1 of)	NA	-4 to 0	1 to 4		5 to 24	25 onwards					
Study Day		-28 to -1	1 to 28		29 to 168	169 onwards					
Day of cycle	NA		1	8	15	22	1				
Visit window			±1 day		±3 days	±3 days	Within 7 days of the final dose of the last IP	±7 days	±7 days	± 7 days	
Informed consent for MET status testing	X										5.1
Retrieve or collect tumour tissue for MET status testing	X ^e										5.1 and 8.6
Blood sample for ctDNA for diagnostic development) ^d	X	X									8.6
Confirm tumour harbours EGFRm (exon 19 deletion and/or L858R)	X ^f										5.1
Informed consent for main study		X									5.1
Inclusion/exclusion criteria		X									5.1 and 5.2

Visit	Pre-screening	Screening	Treatment Period						Follow-up ^a				Details in CSP section	
			Cycle 1 (28-day cycle)			Cycles 2 to 6 (28-day cycle)	Cycle 7 onwards (28-day cycle)	Treatment Discontinuation Visit	28-day Follow-up Visit ^b	Progression Follow-up ^c	Survival Follow up			
Week (Day 1 of)	NA	-4 to 0	1 to 4			5 to 24	25 onwards							
Study Day		-28 to -1	1 to 28			29 to 168	169 onwards							
Day of cycle	NA		1	8	15	22	1	1						
Visit window			±1 day			±3 days	±3 days	Within 7 days of the final dose of the last IP	±7 days	±7 days	± 7 days			
Routine clinical procedures														
Demography	X												5.1	
Physical examination		X	X	X	X	X	Every visit	X					8.2.2	
Height		X											8.2.3	
Weight		X ^g	X				Day 1 of every cycle	Every 8 weeks	X				8.2.3	
Medical/surgical history and comorbid conditions	X	X											5.1	
ECOG/WHO performance score		X	X	X	X	X	Day 1 of every cycle		X	X			5.1	
Vital signs		X	X	X	X	X	Day 1 of every cycle		X	X			8.2.3	
Triplectate ECG		X	X	X	X	X	Day 1 of every cycle Cycle 3 Day 1 ^t		X	X ^h			8.2.4	
MUGA/ECHO		X	Q12W (±2 weeks) relative to randomisation (patients recruited under CSP v7.0) or first dose of study drug (patients recruited prior to CSP v7.0)						X	X ^h			8.2.5	
Concomitant medication and procedures		X	At every visit and may be conducted by phone if not tied to a clinic visit						X	X			6.5	

Visit	Pre-screening	Screening	Treatment Period						Follow-up ^a				Details in CSP section	
			Cycle 1 (28-day cycle)			Cycles 2 to 6 (28-day cycle)	Cycle 7 onwards (28-day cycle)	Treatment Discontinuation Visit	28-day Follow-up Visit ^b	Progression Follow-up ^c	Survival Follow up			
Week (Day 1 of)	NA	-4 to 0	1 to 4			5 to 24	25 onwards							
Study Day		-28 to -1	1 to 28			29 to 168	169 onwards							
Day of cycle	NA		1	8	15	22	1	1						
Visit window			±1 day			±3 days	±3 days	Within 7 days of the final dose of the last IP	±7 days	±7 days	± 7 days			
Routine safety measurements														
Adverse events		X	At every visit and may be conducted by phone if not tied to a clinic visit						X	X			8.3	
Pregnancy test (serum or urine, WOCBP only)		X	Day 1 of every cycle						X				8.2.6	
Safety laboratory assessments (clinical chemistry, haematology and urinalysis)		X	X	X	X	X	Every visit	X					8.2.1	
Coagulation		X											5.1 and 8.2.1	
Liver function tests ⁱ		X	Weekly for the first 10 weeks, then Day 1 of every subsequent cycle						X				8.2.1	
Biomarker analyses														
Blood sample for ctDNA for EGFR mutation alleles and exploratory analysis ^j			Pre-dose on Day 1 and at every subsequent visit in Cycle 1			Day 1 of Cycle 2 and then on occurrence of every RECIST 1.1 scan ^j				X (taken at progression)			8.6	

Visit	Pre-screening	Screening	Treatment Period						Follow-up ^a				Details in CSP section
			Cycle 1 (28-day cycle)			Cycles 2 to 6 (28-day cycle)	Cycle 7 onwards (28-day cycle)	Treatment Discontinuation Visit	28-day Follow-up Visit ^b	Progression Follow-up ^c	Survival Follow up		
Week (Day 1 of)	NA	-4 to 0	1 to 4			5 to 24	25 onwards						
Study Day		-28 to -1	1 to 28			29 to 168	169 onwards						
Day of cycle	NA		1	8	15	22	1	1					
Visit window			±1 day			±3 days	±3 days	Within 7 days of the final dose of the last IP	±7 days	±7 days	± 7 days		
Serum sample for circulating proteins for exploratory analysis		X	X					X					8.6
Genetic sample ^k (optional DNA element for long-term storage/future use)		X											8.7, Appendix D
HLA subtype blood sample			X										8.6
CCI													8.6
Pharmacokinetic measurements													
PK sampling ^{n,o}			X ^o				Day 1 of Cycles 2, 3 and 6 ^o	Day 1 of Cycle 11 ^o					8.5.1

Visit	Pre-screening	Screening	Treatment Period				Follow-up ^a				Details in CSP section	
			Cycle 1 (28-day cycle)		Cycles 2 to 6 (28-day cycle)	Cycle 7 onwards (28-day cycle)	Treatment Discontinuation Visit	28-day Follow-up Visit ^b	Progression Follow-up ^c	Survival Follow up		
Week (Day 1 of)	NA	-4 to 0	1 to 4		5 to 24	25 onwards						
Study Day		-28 to -1	1 to 28		29 to 168	169 onwards						
Day of cycle	NA		1	8	15	22	1					
Visit window			±1 day		±3 days	±3 days	Within 7 days of the final dose of the last IP	±7 days	±7 days	± 7 days		
Efficacy measurements												
Tumour imaging (RECIST Version 1.1) ^p		X ^q	Q6W (±7 days) up to 24 weeks, then every Q8W (±7 days) until objective disease progression relative to randomisation (patients recruited under CSP v7.0) or the first dose of treatment (patients recruited prior to CSP v7.0)								8.1	
EORTC QLQ-C30		X	Q4W (±2 days) relative to randomisation (patients recruited under CSP v7.0) or the first dose of treatment (patients recruited prior to CSP v7.0) ^r				X ^s				8.1.2.1	
QLQ-LC13		X	Weekly (±2 days) in Cycles 1 and 2 and then Q4W (±2 days) relative to randomisation (patients recruited under CSP v7.0) or the first dose of treatment from Cycle 3 onwards (patients recruited prior to CSP v7.0) ^r				X ^s				8.1.2.1	
PGIS		X	Q8W (±2 days) relative to randomisation (patients recruited under CSP v7.0) or the first dose of treatment (patients recruited prior to CSP v7.0) ^r				X ^s				8.1.2.2	
PRO-CTCAE		X	Weekly (±2 days) in Cycles 1 and 2 and then Q4W (±2 days) relative to randomisation (patients recruited under CSP v7.0) or the first dose of treatment (patients recruited prior to CSP v7.0) from Cycle 3 onwards ^s				X ^s				8.1.2.3	

Visit	Pre-screening	Screening	Treatment Period						Follow-up ^a				Details in CSP section
			Cycle 1 (28-day cycle)			Cycles 2 to 6 (28-day cycle)	Cycle 7 onwards (28-day cycle)	Treatment Discontinuation Visit	28-day Follow-up Visit ^b	Progression Follow-up ^c	Survival Follow up		
Week (Day 1 of)	NA	-4 to 0	1 to 4			5 to 24	25 onwards						
Study Day		-28 to -1	1 to 28			29 to 168	169 onwards						
Day of cycle	NA		1	8	15	22	1	1					
Visit window			±1 day			±3 days	±3 days	Within 7 days of the final dose of the last IP	±7 days	±7 days	± 7 days		
EQ-5D-5L		X	Q4W (±2 days) relative to randomisation (patients recruited under CSP v7.0) or the first dose of treatment (patients recruited prior to CSP v7.0) ^f						X ^s				8.1.2.4
Study treatment administration													
Dose with osimertinib or placebo to osimertinib			X (daily dosing)										6
Dose with savolitinib			X (daily dosing)										6
Survival follow up													
Survival status ^u												Q12W	8.1.3
Subsequent anti-cancer treatment												Q12W	8.1.3

^a The follow up period is only applicable for those who discontinue allocated/ randomised treatment and do not cross over to treatment with savolitinib plus osimertinib. Patients who cross over are to carry on assessments as per the SoA in [Table 2](#).

^b As a minimum, telephone contact should be made with the patient 28 days following the discontinuation of both IPs to collect new AEs and follow up on any ongoing AEs and concomitant medications (including any subsequent cancer therapy, if appropriate).

- c At the investigator's discretion, study treatment may continue after progression if a patient continues to derive clinical benefit per guidelines. Patients who continue on treatment following progression should maintain the schedule of assessments at each cycle (28 days): Routine safety measurements (AEs, safety laboratory assessments [clinical chemistry, haematology and urinalysis], and creatinine clearance calculation) and Routine clinical procedures (physical exam, WHO PS, vital signs, Echo/multi-gated acquisition (MUGA), and concomitant medications). In addition, patients will continue to be followed up for survival status every 12 weeks until death, or withdrawal of consent.
- d Refer to Laboratory Manual for details of sample processing for blood sample for ctDNA analysis for diagnostic development; at Pre-screening collect 30 mL blood; at Screening collect 20 mL blood. If a patient is repeating Pre-screening following an interval during which the patient was treated with another EGFR TKI, a repeat blood sample for ctDNA analysis for diagnostic development should be collected.
- e Under CSP version 7.0, only patients with central MET IHC+ and/or FISH+ status will be eligible to Screening; patients with MET status confirmed by local NGS are not eligible. Testing for MET-amplification and overexpression in tumour by FISH (centrally) and by IHC (centrally) will be performed on a tumour sample collected after progression of previous osimertinib treatment. Testing must be performed as initial prescreening with consent obtained using the Pre-screening ICF in advance of obtaining consent for the main study. Approximately **CCI** [redacted] freshly cut (within **CCI** [redacted] days) unstained sections (**CCI** [redacted] micron) from FFPE tissue blocks or FFPE blocks containing equivalent material will be required for all patients. Samples **CCI** [redacted] years old will not be accepted. New samples should only be taken specifically for Pre-screening for this study where the expected risk of an adverse event related to the procedure is <2%.
- f EGFRm status is an inclusion criterion and part of disease diagnosis; prospective central testing is not required.
- g For those patients treated on weight-based dosing regimen for savolitinib (prior to introduction of 300 mg od savolitinib dose for all new patients in CSP version 3.0), the weight captured at Screening will be used to determine the assigned dose.
- h A 28-day follow-up assessment will be required if an on-treatment assessment was abnormal at the time of discontinuation of study therapy to confirm reversibility of the abnormality.
- i Liver function tests will be performed weekly for the first 10 weeks (ie, Day 1, Day 8, Day 15 and Day 22 in Cycle 1 and Cycle 2; then Day 1 and Day 8 of Cycle 3). Where a liver function test is the only assessment, a clinic visit is not required as the test may be performed offsite. In the case of elevated liver function tests, please refer to Appendix I 3.3 for enhanced monitoring and management procedures.
- j At all visits, **CCI** [redacted] blood for plasma is required for ctDNA to measure clearance of EGFR mutation alleles and for exploratory analysis. Blood samples for ctDNA analyses requested on occurrence of every RECIST 1.1 scan should be collected on the day of the scan. If this is not possible the blood sample should be collected as close as possible to the scan within a window of ± 7 days.
- k If not taken at screening the sample may be taken at any visit until the final study visit.
- l Pre-screening tumour sample is to be collected after progression on previous osimertinib treatment and is required during Pre-screening as described in the Laboratory Manual.
- m **CCI** [redacted] for savolitinib and is optional.
- n Date and time of last osimertinib dose prior to Cycle 1 Day 1 (prior to PK sample) will be collected. In addition, date and time of last osimertinib dose and last savolitinib dose prior to each PK sample will be collected.

- Plasma concentrations of osimertinib, savolitinib and their metabolites. Collected on: Cycle 1, Day 1: predose, 1 and 3 hours postdose; Cycle 2, Day 1; predose, 1 and 3 hours post-dose; Cycle 3 Day 1: pre-dose, 1, 3, 4 and 6 hours post-dose; Cycles 6 and 11, Day 1: predose only. PK sample collection windows are: Pre-dose, up to 2 hours pre-dose; 1 hour post-dose, ±5 minutes; 3, 4, and 6 hours post-dose, ±10 minutes. For patients receiving twice daily dosing (savolitinib 300 mg bid), PK samples will be collected following the first dose of the day.
- Patients who discontinue study drug for reasons other than investigator-confirmed disease progression will continue RECIST 1.1 tumour assessments every 6 weeks (±7 days) until Cycle 7 (ie, 24 weeks) and then every 8 weeks (±7 days) (relative to randomisation [patients recruited under CSP v7.0] or the first dose of treatment [patients recruited prior to CSP v7.0]) until objective disease progression per RECIST 1.1 as assessed by the investigator, unless they withdraw consent to the entire study. At the same time points, vital signs, ECGs, and plasma samples for ctDNA will be collected. SAEs considered related to study treatment and/or study procedures will be collected throughout progression follow-up.
- At screening the MRI/CT scans will include brain imaging (MRI preferred) for all patients randomised under CSP version 7.0. Those determined to have brain metastases at baseline or those who had a history of brain metastases will have their brain rescanned (using the same modality as at baseline) at all subsequent tumour assessments until RECIST 1.1-defined PD (including PD). In patients without brain metastases at baseline and without a history of brain metastases, brain scans will be performed only when there is a suspected CNS progression and at the RECIST 1.1-defined extracranial progression. The brain scan is required for all patients at PD by investigator assessment per RECIST 1.1 and should be performed within 4 weeks, but preferably as soon as possible, to allow the assessment of new lesions in the brain.
- ePRO (Electronic devices; LogPads) must be assigned to patients confirmed as eligible for the study, following registration in IWRS after which the device may be taken home by the patient: baseline ePROs must be completed by patients prior to dosing on Cycle 1 Day 1. Screening ePRO assessments offer the opportunity for site staff to set up the device, add the patient, and for the patient to practice reporting ePROs for the first time and make themselves familiar with the device before the baseline assessment at Cycle 1 Day 1. PRO-CTCAE will be administered only in the languages where a linguistically validated version exists. LogPads used for ePRO collection should be returned to site at the nearest visit as soon as the last assessment is completed by patient.
- For patients on the savolitinib 300 mg bid + placebo arm who are eligible for cross over to the savolitinib 300 mg + osimertinib combination arm, the ePRO must be completed after progressive disease is assessed and confirmed by the Investigator, and before crossing over to the combination arm (within 7 days of the final dose of savolitinib + placebo).
- Triplicate ECGs will be required on Cycle 3 Day 1 collected to coincide with collection of blood samples for assessment of PK of osimertinib and savolitinib at this visit.
- Patients will be contacted for survival follow-up every 12 weeks until death, withdrawal of consent or the end of the study ie, at the time of final analysis. Patients should be contacted in the week following the data cut-offs to provide complete survival data. SAEs considered related to study treatment will be collected throughout survival follow-up.

AE Adverse event; bid twice daily; CSP Clinical Study Protocol; ctDNA Circulating tumour deoxyribonucleic acid; CNS Central nervous system; CT Computed tomography; CTSQ-16 Cancer Therapy Satisfaction Questionnaire-16; DNA Deoxyribonucleic acid; ECG Electrocardiogram; ECHO Echocardiogram; ECOG Eastern Cooperative Oncology Group; EGFR Epidermal growth factor receptor; EORTC-QLQ-C30 European Organisation for Research and Treatment of Cancer Quality of Life Questionnaire-Core 30; ePRO electronic patient reported outcomes; EQ-5D-5L EuroQol 5 dimensions, 5 levels; FACT-L Functional Assessment of Cancer Therapy – Lung Cancer; HLA human leukocyte antigen; IHC Immunohistochemistry; IP Investigational product; IWRS Interactive Web Response System; MET Mesenchymal epithelial transition factor; MRI Magnetic resonance imaging; MUGA Multi-gated acquisition; NA Not applicable; NGS Next generation sequencing; PD Progressive disease; PK Pharmacokinetics; PRO-CTCAE Patient reported outcomes version of the Common Terminology Criteria for Adverse Events; Q4W Every 4 weeks; Q6W Every 6 weeks; Q8W Every 8 weeks; Q12W Every 12 weeks; QLQ-LC13 Quality of Life Questionnaire-Lung Cancer 13; RECIST 1.1 Response Evaluation Criteria in Solid Tumours version 1.1; TKI Tyrosine kinase inhibitor; WHO World Health Organization; WOCBP Women of child-bearing potential.

Schedule of activities (SoA) for patients who cross over

Table 2 Schedule of activities for patients who cross over to savolitinib plus osimertinib from savolitinib plus placebo

Crossover Visit	Prior to crossover	Crossover Period			Follow-up				Details in CSP Section
		Cycle 1 (28-day cycle)		Cycles 2 to 6 (28-day cycle)	Cycle 7 onwards (28-day cycle)	Treatment Discontinuation Visit	28-day Follow-up visit ^a	Progres- sion Follow- up ^b	
Week (Day 1 of)		1 to 4		5 to 24	25 onwards				
Study day of crossover		1 to 28		29 to 168	169 onwards				
Day of cycle	1 8 15 22	1		1					
Visit window	NA	± 1 day		± 3 days	± 3 days	Within 7 days of the final dose of the last IP	± 7 days	± 7 days	± 7 days
Informed consent for crossover	X								
Routine clinical procedures									
Physical examination		X			Every visit	X			8.2.2
Weight		X			Day 1 of every cycle	Q8W	X		8.2.3
ECOG/WHO performance score		X			Day 1 of every cycle		X		5.1
Vital signs		X			Day 1 of every cycle		X		8.2.3
Triplett ECG		X			Day 1 of every cycle		X ^c		8.2.4
MUGA/ECHO		Q12W (±2 weeks) relative to crossover C1D1				X	X ^c		8.2.5
Concomitant medication and procedures		At every visit, and may be conducted by phone if not tied to a clinical visit				X	X		6.5

Crossover Visit	Prior to crossover	Crossover Period			Follow-up				Details in CSP Section
		Cycle 1 (28-day cycle)		Cycles 2 to 6 (28-day cycle)	Cycle 7 onwards (28-day cycle)	Treatment Discontinuation Visit	28-day Follow-up visit ^a	Progression Follow-up ^b	
Week (Day 1 of)		1 to 4		5 to 24	25 onwards				
Study day of crossover		1 to 28		29 to 168	169 onwards				
Day of cycle	1 8 15 22			1	1				
Visit window	NA	± 1 day		± 3 days	± 3 days	Within 7 days of the final dose of the last IP	± 7 days	± 7 days	± 7 days
Routine safety measurements									
Adverse events		At every visit, and may be conducted by phone if not tied to a clinical visit					X	X	
Pregnancy test (serum or urine, WOCBP only)		Day 1 of every cycle					X		
Safety laboratory assessments (clinical chemistry, haematology and urinalysis) ^d		X ^d			Every visit	X			8.2.1
Liver function tests ^e		Weekly for the first 10 weeks of the study as per Table 1 ^e , then Day 1 of every subsequent cycle					X		8.2.1

Crossover Visit	Prior to crossover	Crossover Period			Follow-up				Details in CSP Section				
		Cycle 1 (28-day cycle)		Cycles 2 to 6 (28-day cycle)	Cycle 7 onwards (28-day cycle)	Treatment Discontinuation Visit	28-day Follow-up visit ^a	Progression Follow-up ^b					
Week (Day 1 of)		1 to 4		5 to 24	25 onwards								
Study day of crossover		1 to 28		29 to 168	169 onwards								
Day of cycle	1 to 4	1	8	15	22	1	1						
Visit window	NA	± 1 day		± 3 days	± 3 days	Within 7 days of the final dose of the last IP	± 7 days	± 7 days	± 7 days				
Biomarker analyses													
Blood sample for ctDNA for EGFR mutation alleles and exploratory analysis ^f		Pre-dose on Day 1 and Day 22 in Cycle 1		Day 15 of Cycle 2					8.6				
Serum sample for circulating proteins for exploratory analysis						X			8.6				
CCI									8.6				
Efficacy measurements													
Tumour imaging (RECIST 1.1) ^b		Scheduled imaging is required for patients who cross over based on a declaration of futility of the savolitinib monotherapy arm and who have not progressed during the initial randomised treatment period: Q6W (±7 days) up to 24 weeks relative to initial randomisation, then every Q8W (±7 days) until objective disease progression							8.1				

Crossover Visit	Prior to crossover	Crossover Period			Follow-up				Details in CSP Section
		Cycle 1 (28-day cycle)	Cycles 2 to 6 (28-day cycle)	Cycle 7 onwards (28-day cycle)	Treatment Discontinuation Visit	28-day Follow-up visit ^a	Progression Follow-up ^b	Survival Follow-up	
Week (Day 1 of)		1 to 4		5 to 24	25 onwards				
Study day of crossover		1 to 28		29 to 168	169 onwards				
Day of cycle	1 to 4	1	8	15	22	1	1		
Visit window	NA	± 1 day		± 3 days	± 3 days	Within 7 days of the final dose of the last IP	± 7 days	± 7 days	± 7 days
Study treatment administration									
Dose with osimertinib		X (daily dosing)							6
Dose with savolitinib ⁱ		X (daily dosing)							6
Survival follow-up									
Survival status ^j									Q12W 8.1.3
Subsequent anti-cancer treatment									Q12W 8.1.3

^a As a minimum, telephone contact should be made with the patient 28 days following the discontinuation of both IPs to collect new AEs and follow up on any ongoing AEs and concomitant medications (including any subsequent cancer therapy, if appropriate).

^b At the investigator's discretion, study treatment may continue after progression if a patient continues to derive clinical benefit per guidelines. Patients who continue on treatment following progression should maintain the schedule of assessments at each cycle (28 days): Routine safety measurements (AEs, safety laboratory assessments [clinical chemistry, haematology and urinalysis], and creatinine clearance calculation) and Routine clinical procedures (physical exam, WHO PS, vital signs, Echo/multi-gated acquisition (MUGA), and concomitant medications). In addition, patients will continue to be followed up for survival status every 12 weeks until death, or withdrawal of consent.

^c A 28-day follow-up assessment will be required if an on-treatment assessment was abnormal at the time of discontinuation of study therapy to confirm reversibility of the abnormality.

^d The frequency of safety laboratory assessments will depend on the timepoint at which the patient crosses over. Safety laboratory assessments should be performed weekly on Days 1, 8, 15, and 22 during the first 4 weeks of the study (ie, for patients who cross over prior to completing the first 4 weeks of the study) then every subsequent cycle visit in the crossover period.

- c The frequency of liver function tests will depend on the timepoint at which the patient crosses over. Liver function tests should be performed weekly for the first 10 weeks of the study (ie, for patients who cross over prior to completing 10 weeks of the study) then on Day 1 of every subsequent cycle in the crossover period. Where a liver function test is the only assessment, a clinic visit is not required as the test may be performed offsite. In the case of elevated liver function tests, please refer to Appendix I 3.3 for enhanced monitoring and management procedures.
- f At all visits, [REDACTED] mL blood for plasma is required for ctDNA to measure clearance of EGFR mutation alleles and for exploratory analysis.
- g **CCI** [REDACTED] for savolitinib and is optional.
- h For patients who cross over based on confirmed objective disease progression during the initial randomised treatment period, scheduled RECIST 1.1 tumour assessments are not required, and the subsequent assessment of disease progression will be based on standard-of-care scan or investigator determined clinical progression. Scheduled RECIST 1.1 tumour assessments are required (the scan frequency is against initial randomisation) for patients who cross over based on a declaration of futility of the savolitinib monotherapy arm and who have not objectively progressed during the initial randomised treatment period. Patients who cross over based on a declaration of futility, who have no objective progression during initial randomisation period, and who discontinue study drug after cross-over for reasons other than investigator-confirmed disease progression will continue scheduled RECIST 1.1 tumour assessments until objective disease progression per RECIST 1.1 as assessed by investigator, unless they withdraw consent to the entire study. At the same time points, vital signs, and ECGs will be collected. SAEs considered related to study treatment and/or study procedures will be collected throughout progression follow-up.
- i Patients who cross over must not receive any other anti-cancer therapies between the assessment of PD and the addition of osimertinib. Savolitinib treatment should continue uninterrupted during this period.
- j Patients will be contacted for survival follow-up every 12 weeks until death, withdrawal of consent or the end of the study ie, at the time of final analysis. Patients should be contacted in the week following the data cut-offs to provide complete survival data. SAEs considered related to study treatment will be collected throughout survival follow-up.

AE Adverse event; bid twice daily; C Cycle; C1D1 Cycle 1 Day 1; CSP clinical study protocol; ctDNA Circulating tumour deoxyribonucleic acid; D Day; DNA Deoxyribonucleic acid; ECG Electrocardiogram; ECHO Echocardiogram; ECOG Eastern Cooperative Oncology Group; EGFR Epidermal growth factor receptor; IP Investigational product; MUGA Multi-gated acquisition; NA Not applicable; PD progressive disease; PK Pharmacokinetics; Q6W Every 6 weeks; Q8W Every 8 weeks; Q12W Every 12 weeks; RECIST Response Evaluation Criteria in Solid Tumours; SAE Serious adverse event; WHO World Health Organization; WOCBP women of child-bearing potential.

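### The schedule footnotes for patients treated beyond progression omit ECG and pregnancy testing and place Echo/MUGA at every cycle, against the schedule rows and Sections 8.2.5 and 8.2.6

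*Protocol*

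**What the plan says.** Protocol Sections 4.1.1 and 7.1 allow patients with continuing clinical benefit to remain on the combination, or on osimertinib alone, beyond RECIST 1.1 progression. Within the schedule of activities, the text written for them is Table 1 footnote c and, for crossover patients, Table 2 footnote b. Both say: "Patients who continue on treatment following progression should maintain the schedule of assessments at each cycle (28 days"). A list in two blocks follows:

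- The safety block has AEs, then "safety laboratory assessments [clinical chemistry, haematology and urinalysis], and creatinine clearance calculation".
- The clinical block reads "Routine clinical procedures (physical exam, WHO PS, vital signs, Echo/multi-gated acquisition (MUGA), and concomitant medications").

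The on-treatment rows of Table 1 say:

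- Triplicate ECG: "Day 1 of every cycle Cycle 3 Day 1", the last part being the extra ECGs tied to PK sampling.
- "Pregnancy test (serum or urine, WOCBP only"): Day 1 of every cycle, repeated in Section 8.2.6.
- MUGA/ECHO: "Q12W (±2 weeks) relative to randomisation (patients recruited under CSP v7.0) or first dose of study drug (patients recruited prior to CSP v7.0"). Section 8.2.5 gives the same interval.

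Table 2 has the same frequencies, with MUGA/ECHO counted from the first crossover dose.

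**The concern.** The footnote gives a frequency and then a named list, with nothing to mark the list as a set of examples. Two on-treatment assessments are missing from it and a third appears at a different frequency from its row. A coordinator looking up what a patient dosed beyond progression needs will find this note first.

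The missing items are safety monitoring. Appendix I 3.5 treats QTc prolongation as an overlapping toxicity of osimertinib and savolitinib. The Grade 3 hold rule in Table 12 requires QTcF above 500 msec on at least two separate ECGs, so it works only if ECGs are taken. Pregnancy requires immediate discontinuation, and the per-cycle test is the scheduled means of detecting it. There is also a reporting consequence. SAP Section 4.2.3.4 counts QTcF excursions at any point on treatment, so ECGs skipped after progression would be missing from that table. In the other direction, echocardiography at every cycle would be an unneeded burden.

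**Working it through.** The plan gives no figure to reproduce. The check compares the footnote list with the rows and then counts assessments.

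**Coverage of the list.** The footnotes name two blocks of the schedule. The on-treatment rows in those blocks, the same in Tables 1 and 2, are:

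- Clinical, 7 rows: physical examination, weight, ECOG/WHO status, vital signs, triplicate ECG, MUGA/ECHO, concomitant medication.
- Safety, 4 rows: AEs, pregnancy test, safety laboratory tests, liver function tests.

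Total: 7 + 4 = 11. The list names 7 of these outright: AEs, safety laboratory tests, physical examination, performance status, vital signs, Echo/MUGA and concomitant medication. Liver function tests can be counted under clinical chemistry (Table 10) and weight under vital signs (Section 8.2.3), giving 7 + 2 = 9. The remaining 11 − 9 = 2 are triplicate ECG and pregnancy test.

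The list is not a shortened copy of the rows either. It names a creatinine clearance calculation that has no row in either table. That value can be derived from serum creatinine, so it needs no change.

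**Counts per patient.** Row interval for ECG and pregnancy test: 28 days. Row interval for ECHO/MUGA: 12 × 7 = 84 days. Literal footnote interval for Echo/MUGA: 28 days. The counts are for ordinary later cycles, leaving out the weekly Cycle 1 ECGs and the extra Cycle 3 ECGs.

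| Assessment | 12 weeks (84 days): rows | 12 weeks: footnote taken literally | 24 weeks (168 days): rows | 24 weeks: footnote taken literally |
|---|---|---|---|---|
| Triplicate ECG sets | 84/28 = 3 (3 × 3 = 9 tracings) | 0 | 168/28 = 6 | 0 |
| Pregnancy tests, where applicable | 84/28 = 3 | 0 | 168/28 = 6 | 0 |
| Echo/MUGA | 84/84 = 1 | 84/28 = 3 | 168/84 = 2 | 168/28 = 6 |

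**Whether other text settles the conflict.** For ECHO/MUGA and pregnancy tests, Sections 8.2.5 and 8.2.6 state the frequency independently and agree with the rows. For ECG, Section 8.2.4 gives no frequency and refers to the schedule. Section 7.1 (osimertinib alone beyond progression) and Appendix I 3.5 also refer to the schedule, and Section 2.3.1 refers to the study plan. Because the conflict sits inside the schedule, these references do not resolve it. SAP Section 3.2.2.5 restates ECG on Day 1 of each later cycle, but sites do not work from the SAP. No text exempts these patients from ECG or pregnancy testing, and nothing outside the two footnotes suggests echocardiography every 4 weeks.

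**The case against.** The strongest reply is that the footnote tells sites to keep the existing schedule, and that the list does not displace it.

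- Neither footnote contains a waiver or a word such as *only*.
- Footnote c hangs on the progression follow-up column, while footnote a says "The follow up period is only applicable for those who discontinue allocated/ randomised treatment". A patient still dosing therefore stays in the treatment columns, where ECG and pregnancy test remain scheduled.
- The imaging row carries a stop, "until objective disease progression relative to randomisation (patients recruited under CSP v7.0"), and the ECG and pregnancy rows carry none. The protocol states a progression cut-off where it wants one.
- Section 2.3.1 and Appendix I 3.5 expect ECGs throughout the study.
- Most crossover patients have already progressed on randomised treatment, yet the Table 2 rows still schedule ECG and pregnancy test every cycle.
- Table 1 footnote p and Table 2 footnote h ask for ECGs at scan times in certain patients who have stopped study drug before progression. It would be odd to intend none for patients still taking it.
- Table 12 requires regular ECGs once a Grade 3 prolongation has been found, whatever the progression status.

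Most of this stands, and it makes the row schedule the better reading. It does not remove the conflict. The footnote p comparison also cuts the other way: the protocol names ECGs in footnotes when it wants them, so a site could take their absence here as deliberate. The Table 12 follow-up begins only after a prolonged QTcF has been detected, which is the purpose of the scheduled ECG.

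**Conclusion.** The concern holds as a minor inconsistency in the safety schedule. Two footnotes written for patients treated beyond progression disagree with the schedule rows on three assessments, and with Sections 8.2.5 and 8.2.6 on two of them. Its size depends on how a site reads the footnotes. On a literal reading, the per-patient differences are those tabulated above. If the site continues the row schedule, the difference is zero for all three. The documents do not say how many patients are treated beyond progression, so no study total can be given. The count of nine covered rows rests on placing liver function tests under clinical chemistry and weight under vital signs. The ORR analyses, sample size and efficacy methods are unaffected. The only analysis exposed is the on-treatment QTcF summary.

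**What to change.** In Table 1 footnote c and Table 2 footnote b, add triplicate ECG on Day 1 of every cycle and, for women of childbearing potential, a pregnancy test on Day 1 of every cycle. State ECHO/MUGA as every 12 weeks (±2 weeks).

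The cost is two reworded footnotes. All three assessments already sit in the on-treatment rows at these frequencies, so nothing is added to the row schedule. PRO and PK assessments are untouched.
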